## LIST OF ABBREVIATIONS

COI	Conflict of Interest
CRF	Case report form
HIPAA	Health Insurance Portability Accountability Act
ICD	Informed Consent Document
IRB	Institutional Review Board
OHIP	Oral Health Impact Profile
OHRP	Office of Human Research Protections
OPRS	Office for the Protection of Research Subjects
PHI	Protected Health Information
PI	Principal Investigator
SAE	Serious Adverse Event
UIC	University of Illinois at Chicago

## 1.0 Project Summary/Abstract

Recent studies suggest a positive association between the volume of the peri-implant mucosa (“*gum*” *tissue*) surrounding a dental implant and the ultimate health and appearance of a dental implant supported crown (“*implant*”). The use of a gum allograft (e.g., PerioDerm®) at the time implant placement has been advocated to increase the volume of mucosa to avoid the morbidity of autogenous soft tissue grafting from the patient’s palate [1]. However, the evidence supporting this is limited and properly controlled, prospective trials are lacking. Despite this, many clinicians already use gum allografts during implant therapy.

The purpose of this study is to prospectively evaluate whether including a gum allograft during implant therapy enhances the implant health and appearance.

## 2.0 Background/Scientific Rationale

An alveolar ridge is the part of the jaw bone which immediately surrounds and anchors the tooth socket (“*alveolus*”). Similar to any bone or muscle atrophying when not used, the alveolar ridge will shrink (“*resorb*”) following tooth extraction. The volume of an alveolar ridge can be measured by 3D intraoral scanning, and is used clinically as a metric of oral health.

A **dental implant** is a titanium screw shaped implant placed into the healed alveolar bone or tooth socket following tooth extraction. It replaces the tooth root and supports the crown that is attached to an abutment. The abutment is surrounded by peri-implant mucosa that protects underlying bone and provides esthetic contour for the artificial tooth.

An **abutment** is a titanium or zirconia transmucosal component that is screwed onto the implant and is designed to connect the crown to the implant. A **crown**, also referred to as a “dental cap”, is an artificial tooth generally made with porcelain or surgical grade metals such as gold or titanium.

Osseointegration is the development of a functional and structural connection between the alveolar ridge of the jaw and the dental implant. Implant success requires both sufficient bone volume for osseointegration and sufficient mucosal tissue to protect against biofilm mediated inflammation, assure functional comfort and contribute to dental implant esthetics. Our own research has demonstrated that following dental implant placement in healed ridges or extraction sockets, the alveolar ridge continues to resorb approximately 0.5 to 1.0 mm during the first year of healing [2]. Healed ridges are also often volumetrically deficient, having lost approximately 30% of their horizontal volume following tooth extraction [3].

To account for this loss in peri-implant architecture, peri-implant mucosal bone grafting has been proposed and is currently part of dental implant therapy. Both autogenous grafts (*mucosal connective tissue from the roof of the patient’s own mouth or “palate”*) and allogeneic grafts (*collagen-rich grafts derived from a genetically non-identical human donor*) are used for these purposes, but there is controversy regarding the effectiveness of this supplemental graft during implant treatment [4-7]. Xenograft mucosal materials are grafts from non-human donors. Popular

in Europe where allograft materials are not widely used and used for soft tissue augmentation at implants, xenografts have successfully increased soft tissue thickness and volume in a stable manner [8]. These studies have typically employed linear (2D) measures to study outcomes. When volumetric (3D) measures have been employed, positive effects were not observed [9]. Using 3D measurement to assess outcomes of soft tissue augmentation at the time of implant is viewed as essential to the proper architectural evaluation of this clinical intervention [10].

The studies cited above attest to the safety and efficacy of soft tissue grafting at implants. These studies have not indicated that soft tissue grafting at implants increases the risk of implant failure. Further, there is evidence that increased thickness of soft tissue enhances the patients' comfort when performing oral hygiene and reduces associated signs of inflammation such as bleeding on probing. These cited studies further revealed no incidence of untoward morbidity or associated complications.

The general conclusion of a recent systematic review concerning the effects of soft tissue augmentation procedures on peri-implant health or disease were: 1) favorable peri-implant health, 2) increased keratinized mucosa, 3) reduced bleeding on probing, 4) less marginal bone loss with increased mucosal thickness. These advantages were reported in 10 articles, however, only 4 studies were randomized controlled trials [11]. Unfortunately, this review did not include any studies that have used allogeneic materials such as that proposed here. Thus, the present literature identifies both an important gap in knowledge regarding the use of allogenic materials for soft tissue augmentation at dental implants and relatively little volumetric assessment of any soft tissue augmentation procedure. The existing literature indicates that the placement of a submucosal connective tissue allograft is not associated with increased risks of implant failure or increased complications.

In this study, we will compare the clinical outcomes of placing a submucosal graft material in front of the dental implant immediately after placement of the implant (Figure 1). This soft tissue augmentation will be evaluated by comparison to implants placed without augmentation. An example of the significance of such a study is illustrated in Figure 2 that shows a healthy implant with sufficient soft tissue (top) and an unesthetic and inflamed implant with soft tissue recession (bottom). This can be prevented by increasing the thickness of the peri-implant mucosa using allogenic graft materials.

Figure 1

[figure not shown]

Figure 2

### 3.0 Objectives/Aims

The purpose of this research is to investigate changes in the health and appearance of oral tissues in patients receiving an artificial gum graft at the time of dental implant placement. Specifically, we want to know if adding a PerioDerm® allograft along with the dental implant will improve the health and appearance of a dental implant with a crown.

The anticipated study duration is approximately 18 months involving 6 months of recruitment and 12 months of treatment and evaluation.

### 4.0 Eligibility

The subject population will be:

- a. Patients at the UIC Dental School who desire placement of a dental implant for an already missing tooth or
- b. Patients at the UIC Dental School who desire placement of a dental implant for a tooth that will soon be extracted or
- c. Patients in the community who desire placement of a dental implant for an already missing tooth or for a tooth that will soon be extracted.

Subject eligibility at UIC will be assessed and determined by the UIC PI with assistance from authorized UIC study co-investigators (Co-Is) and coordinators.

#### 4.1 Inclusion Criteria

Patients within the UIC Dental School and the community who are:

- at least 18 years of age and
- willing and able to provide informed consent.
- in need of one implant to replace a missing tooth
- at least 20 teeth in good repair and occlusion
- Sufficient bone volume for dental implant placement without required bone augmentation

- Site development (soft and/or bone tissue) performed at least 5 months before implant placement, when required

#### **4.2 Exclusion Criteria**

- Implant cannot be placed without bone graft
- Unable to pay for crown
- Current smoker
- Untreated rampant caries and uncontrolled periodontitis
- Current alcohol or drug abuse
- Absence of adjacent (mesial and/or distal) natural tooth
- Uncontrolled diabetes
- Systemic or local disease or condition that would compromise post-operative healing and/or osseointegration
- Use of bisphosphonates
- History of radiation in the head and neck region
- Unable or unwilling to return for follow-up visits
- Unrealistic esthetic or functional demands
- Unlikely to be able to comply with study procedures
- Unwilling or unable to provide informed consent

#### **4.3 Excluded or Vulnerable Populations**

Vulnerable populations (minors, pregnant women, prisoners) will not be targeted in this study.

#### **5.0 Subject Enrollment**

Subjects will be screened by the UIC PI, UIC Co-I and/or authorized UIC study personnel at the UIC College of Dentistry Clinical Research Center. Dental AxiUm records may be reviewed for recruitment purposes. Patients attending the UIC Dental Clinic who desire implant therapy will be examined per standard of care; those found eligible for dental implant therapy will also screened for possible study inclusion.

[figure not shown]
Recruitment flyers may be posted on campus and on the websites of both UIC and the Chicago Dental Society. A recruitment email may be periodically be released on the UIC campus listserve. Interested patients will be instructed to contact the College of Dentistry Clinical Research Center (COD-CRC) to set up a screening appointment where the informed consent discussion and confirmation of study eligibility will occur. Target enrollment will be 40 subjects, but up to 60 subjects may be enrolled if needed to account for screening failures.

#### **6.0 Study Design and Procedures**

This will be a randomized interventional study of PerioDerm® gum allograft (“+Graft”) plus standard dental implant with crown therapy versus standard dental implant with crown therapy alone (“-Graft”).

## Study Outcomes:

- Primary outcomes will be volume of the alveolar ridge at 12 months as measured by 3D intraoral scanning.
- Secondary outcomes will be implant survival, bleeding upon probing, marginal bone levels (MBLs) as measured by peri-apical radiographs and patient satisfaction as measures by the OHIP patient survey.

The research study will be performed at the UIC Dental School Clinical Research Center and will involve multiple clinic visits. These clinic visits usually occur at the same time as the subjects clinic visits for implant therapy, to avoid any research-only visits. The schedule for obtaining a dental implant is shown above in Figure 1 in blue with research visits shown in green and is described below:

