## **7.0 Expected Risks/Benefits**

The risks of dental implant therapy are minimal but include complications such as bleeding and bruising after surgery, post-surgical pain, infection, delayed healing, temporary speech problems, bone fracture, temporary or permanent damage to the nerves of the jaw, loss of bone on the upper or lower jaw (including altered appearance of the gum line), infection in the bone, damage to the adjacent teeth, chronic pain, abscess, and infection of the gums.

Risks of a PerioDerm® allograft include local or systemic infection, dehiscence (*wound rupture along the line of incision*) and/or necrosis (*death of tissue*) due to poor revascularization or allergic response to some component(s) of the graft material.

In accordance with the graft manufacturer's instructions, tissue recipient records for subjects receiving PerioDerm® will be maintained for the purpose of post-transplant tracing. This may increase the risk to the privacy of subjects randomized to +Graft.

CBCT and other 3D intraoral scanner capture light-generated images which are compiled by the appropriate software into a 3 dimensional geometric image. Since these scanners does not utilize xray technology, the medical risks of use are minimal and include mild fatigue of the facial muscles.

Subjects will be encouraged to contact the PI in the event of medical emergencies related to his/her dental care and will be provided a 24-hour emergency contact number. Subjects experiencing complication may require additional (>5) clinic visits during the course of this study. This is clearly indicated within the consent document.

If implant integration fails or the implant site is infected, the implant will be removed or the site infection treated using standard dental therapies. The subject will be excluded from this study and referred to UIC College of Dentistry for care.

Restoration of the oral cavity is likely to benefit all subjects, irrespective of study group. The potential for an enhanced restoration in the +Graft study group, as compared to the -Graft group, is the focus of this study.

Results from this research may lead to modifications in standards of care which may benefit future patients receiving dental implant therapy.

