## **8.0 Data Collection and Management Procedures**

Each subject will be assigned a unique study ID. Study data will be collected following each clinic visit and recorded on the applicable case report forms (CRFs). Data will be coded to the subject study ID. The Enrollment Log, needed to link a subjects study code to identifiers, will be stored separately. Hard copies of CRFs and the Enrollment Log will be stored in locking file cabinets within the UIC College of Dentistry Clinical Research Center. Electronic documents will be stored on a secure departmental server. Only authorized UIC research personnel will have access.

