## **9.0 Data Analysis**

Data analysis will be performed by the UIC PI in collaboration with the Co-I's using SPSS, SAS or similar software. A biostatistician may be consulted for statistical analysis, if required. Data will be de-identified prior to release to any statistician not listed as study personnel on Appendix P.

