## **10.0 Quality Control and Quality Assurance**

The UIC investigators are clinicians who are trained to perform dental implant therapy (both with and without allografts) at the UIC College of Dentistry. Only trained UIC personnel will participate in the clinical care of UIC subjects.

Study data, including photographic records, hard copy CRFs and the electronic patient records of treatment, will be reviewed periodically by the PI and Coordinator. All investigators will be calibrated to the study protocol in an initiation meeting(s) before undertaking study intervention (visit #2; implant surgery). Outcomes regarding quality of care and records will be reviewed in monthly research team meetings.

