## 12.0 Statistical Considerations

A sample size of 40 subjects is based on previous studies. Our previous investigations of peri-implant mucosal levels have demonstrated that it is possible to distinguish differences of 0.5 mm among groups of 25 subjects. Here, we anticipate augmentation of approximately 1.0 mm – 1.5 mm and should readily determine significant differences between 20 subjects / group. A recent prospective clinical study comparing no graft to a autogenous connective tissue graft demonstrated a significant difference with 20 subjects / group [12]. This study utilized a similar set of inclusion/exclusion criteria and performed a similar intervention. Even a smaller study comparing 8 subjects with grafts to 10 without demonstrated significant 3D volume changes using a similar scanner-based analytic method [13]

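### The sole primary outcome, 12-month ridge volume from 3D scans, has no masking of the reader to arm and no fixed reference scan, region or alignment

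*Combined protocol and SAP*

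**What the plan says.** Section 6.0 (Study Outcomes) gives the full definition of the primary outcome: "Primary outcomes will be volume of the alveolar ridge at 12 months as measured by 3D intraoral scanning". The visit descriptions in Section 6.0 schedule 3D intraoral scans at screening, at about 8 weeks and at about 1 year. None of the three is named as the reference for the primary outcome.

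The nearest text on method is in two places. Section 7.0 says scanner images are "compiled by the appropriate software into a 3 dimensional geometric image". Section 12.0, in support of the sample size, says that a small cited study "demonstrated significant 3D volume changes using a similar scanner-based analytic method [13".

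On data handling, Section 8.0 states "Data will be coded to the subject study ID". Section 9.0 states "Data analysis will be performed by the UIC PI in collaboration with the Co-I's using SPSS, SAS or similar software" and adds "Data will be de-identified prior to release to any statistician not listed as study personnel". Section 11.2 restricts data access to the investigators and authorised team members. Section 10.0 states "Study data, including photographic records, hard copy CRFs and the electronic patient records of treatment, will be reviewed periodically by the PI and Coordinator". It also has investigators calibrated to the protocol before surgery.

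**The concern.** An intraoral scan is a surface image. Someone has to turn it into a ridge volume by choosing where the measured region begins and ends and, if change is wanted, how two scans are superimposed. If those choices are open and the person making them knows the arm, they can drift in favour of one arm without any intent. Randomisation balances subjects at entry; it does not protect a measurement made a year later.

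The plan also states the direction it expects. Section 2.0 says thicker mucosa from allogeneic graft material can prevent recession, and Section 12.0 anticipates augmentation of about 1.0 to 1.5 mm. Open choices combined with a declared expectation are the setting in which masked reading is most useful. At stake is the only listed primary outcome.

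**Working it through.** This is a check of text, so the relevant sections are set against what a protected reading would need.

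**1. Is a reader named or masked?**
- Section 6.0 schedules the scans but names no reader.
- Section 8.0 codes data by study ID. A team member who knows the subject or the record still knows the arm.
- Section 9.0 de-identifies data only for a statistician outside the listed personnel. Removing identity is not removing arm.
- Section 11.2 limits access by team membership, not by arm.
- Section 10.0 has the investigator and the coordinator review treatment records, which would show whether a graft was placed. Section 7.0 adds that tracing records are kept for graft recipients.

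Result: no reader is named, no masking is stated, and at least two team members routinely see records that can reveal the arm.

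**2. Is the measurement fixed?**
- Section 7.0 describes how an image is built, not how a volume is read from it.
- Section 12.0 calls a cited study's method similar. It does not describe that method or adopt it for this trial.
- References 9 and 13 appear to be the same retrospective case-control study. Section 2.0 cites it for positive volumetric effects not being observed; Section 12.0 cites it for significant volume changes. The two uses should be reconciled, and the citation cannot serve as a specification.
- The calibration in Section 10.0 is to the protocol, which contains no reading procedure.

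Result: endpoint form, reference scan, region and alignment are all open.

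**3. Does the open choice matter?** The mouth differs between scans. At screening the tooth may still be present (Section 4.0). At 8 weeks there is a temporary crown or a healing abutment, and at 1 year a final crown (Section 6.0). The graft is placed at visit 2, so change from the screening scan includes the volume added at surgery, while change from the 8-week scan starts after it was added. These are different quantities, and absolute 12-month volume is a third.

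**4. Can the bias be sized?** No. The only quantities in Section 12.0 are linear: 0.5 mm with groups of 25, and 1.0 to 1.5 mm anticipated here. No unit, SD or reading error is given for volume. Any inflated error rate would follow from a shift between arms that had simply been assumed, so none is offered.

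**5. How many scans would be coded?** Target enrolment is 20 per group × 2 = 40 (Sections 5.0 and 12.0).
- 12-month scan only: 40 × 1 = 40
- plus one reference scan: 40 × 2 = 80
- plus both earlier scans: 40 × 3 = 120

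These are upper counts for 40 subjects, assuming no dropout and no exclusion after implant failure.

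**The case against.** The strongest reply is that this is an argument from silence. Some front matter, the figures, the appendices, the case report forms and the cited source were not available, and a reading procedure could sit in one of them. That stands, and it limits the claim to the supplied text. The text describes Figure 1 as showing graft placement and the visit schedule, not a measurement method.

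A reader might also infer that the investigators will read their own patients' scans knowing the arm. The documents do not support that. Section 9.0 concerns statistical analysis, which is not the same task as deriving volumes. In Section 10.0, "The UIC investigators are clinicians who are trained to perform dental implant therapy (both with and without allografts" shows competence in both treatments, not knowledge of a given subject's allocation. The monthly meetings are not said to discuss arms. Only the record review clearly gives access to the arm, and nothing says those who do it will read scans.

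It can further be said that a scan measurement is less subjective than a clinical score, and that tissue contour may reveal a graft even under a code. Both have some force. They limit how much masking can achieve and make the written measurement rules more important, since those help even where masking is imperfect. They do not remove the gap.

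**Conclusion.** The point holds in a limited form. In the supplied text the sole primary outcome is to be derived without stated masking of the reader and without a fixed endpoint form, reference scan, region or alignment. Unmasked reading is permitted, not shown to occur. The size and direction of any bias are unknown, so the stronger conclusion, that the trial's result will be biased towards the graft, does not follow.

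Missing measurement detail alone would be a matter of completeness. What makes the point worth acting on is that the files are digital and can be recoded, so a source of bias in the primary outcome can be reduced without new visits or subjects. It is best classed as a cheap improvement. If a masked reading procedure already exists in a document not supplied, citing it in Section 6.0 would settle the matter.

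**What to change.** Add to Section 6.0, under Study Outcomes:

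> All scans used for the primary outcome are exported under a random reading code with no arm label and read by an existing team member who did not operate on that subject and does not see that subject's treatment record before reading. Before the first reading, the endpoint form (absolute 12-month volume or change), the reference scan, the measured region and the alignment surfaces are fixed in writing and applied identically to both arms. Volumes are locked before arm is merged. Any reading made with knowledge of arm is flagged, and the number by arm is reported with the primary result.

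The last sentence matters in a small team: it allows for an unavoidable unmasked reading but makes the extent visible.

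Cost: a few sentences and the coding of about 40 to 120 scans at target enrolment, with no extra visits or subjects. The documents give neither team size nor anyone's training in volume measurement, so the availability of a suitable existing reader is an assumption. Two downsides remain: the reader must stay out of record review for the subjects concerned until volumes are locked, and tissue contour may still partly reveal the arm.

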### 2. Second visit: ("Implant surgery")

The second visit will be coordinated with usual and customary treatment for dental implant therapy. Prior to implant surgery, subject will be asked to complete the OHIP patient satisfaction questionnaire. This questionnaire is for research purposes only. Additionally, at the second visit, subjects will be randomized (+Graft vs. -Graft) by authorized study personnel and his/her implant, with abutment and temporary crown, will be placed (+/- Graft). The abutment and temporary crown will be placed onto the implant. If this implant is not stable, a healing abutment will be placed instead and a removable temporary will be provided within 24 hours. The experimental variable in this study is placement of a submucosal allograft in randomized patients. PerioDerm® is not an

experimental material and is available for sale and use within the USA (see Appendix A1). This visit will require approximately 2 hours.

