### 6. Sixth visit: ("1 year follow-up")

This final visit will be approximately 1 year post-surgical followup and is performed in accordance with standard of care. Additionally, a 3D intraoral scan will be performed, subject will be asked to complete the OHIP patient satisfaction questionnaire and will receive a \$50 gift card for research purposes.

This visit will require approximately 30 – 60 minutes. Should any complication be observed at this time, appropriate standard of care interventions will be made at that time and the subject will be referred to the UIC College of Dentistry dental clinics or their dentist for further treatment or retreatment.

All 3D intraoral scans are light-based, are not x-ray scans, and utilize scanners sold to and used by dentists in replacement of conventional impressions

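### The primary outcome is named as ridge (bone) volume, but the named scan records outer contour, mucosa and bone together, so it needs redefining and its conclusions limiting to contour

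*Combined protocol and SAP*

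**What the plan says.** The primary outcome in section 6.0 (Study Outcomes) reads: "Primary outcomes will be volume of the alveolar ridge at 12 months as measured by 3D intraoral scanning".

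Section 2.0 gives the term its meaning: "An alveolar ridge is the part of the jaw bone which immediately surrounds and anchors the tooth socket". The same paragraph says: "The volume of an alveolar ridge can be measured by 3D intraoral scanning". Later in section 2.0, bone volume and mucosal tissue appear as two separate requirements for implant success.

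On the instrument, the sixth-visit text in section 6.0 says: "All 3D intraoral scans are light-based, are not x-ray scans". It adds that dentists use these scanners instead of taking conventional impressions.

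On the intervention, the second-visit text in section 6.0 says: "The experimental variable in this study is placement of a submucosal allograft in randomized patients". Section 2.0 describes the aim after showing an implant with soft-tissue recession: "This can be prevented by increasing the thickness of the peri-implant mucosa using allogenic graft materials".

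The only follow-up bone outcome is marginal bone level on peri-apical radiographs, which is secondary. CBCT is listed at the first visit and at no later one.

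**The concern.** The outcome's name refers to one tissue, the instrument measures two together, and the treatment acts on the tissue that the name leaves out. Within the randomised comparison, any graft bulk retained at 12 months counts as ridge volume. If the plan is followed as written, a mucosal gain is reported as an effect on the ridge, which a reader using the protocol's own definition would take to mean bone.

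The distinction matters because section 2.0 cites a systematic review reporting less marginal bone loss where mucosa is thicker. Graft bulk and bone preservation are therefore both possible explanations within the protocol's rationale, and the scan cannot separate them. No section says how bone would be distinguished from mucosa in the scanned volume.

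**Working it through.** The plan contains no figure for this point that can be reproduced. The sample size of 40 rests on previous studies, and no alpha, power or SD is stated. The check therefore sets the statements side by side and then gives two illustrations.

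**Side by side**

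- Quantity named: ridge volume (section 6.0), with ridge defined as bone (section 2.0).
- Quantity recorded: outer contour. This is an inference from the scan being light-based, not x-ray, and a substitute for impressions. The protocol does not use the words surface scan, but the inference is sound.
- Quantity the treatment changes: mucosal thickness (section 2.0; section 6.0, second visit).

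So scanned change = bone change + mucosal change, and the randomised variable acts directly on the second term.

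**Illustration 1: size of the possible mislabelling**

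Inputs:

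- Augmentation G = 1.0 to 1.5 mm (section 12.0).
- First-year resorption R = 0.5 to 1.0 mm. Section 2.0 says "the alveolar ridge continues to resorb approximately 0.5 to 1.0 mm during the first year of healing".

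Assumptions: R is the same in both arms, G and R lie on one axis of the scanned surface, and G is not already net of R.

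- Without graft: −R = −0.5 to −1.0 mm.
- With graft: G − R, from 1.0 − 1.0 = 0.0 mm to 1.5 − 0.5 = +1.0 mm.
- Difference between arms: (G − R) − (−R) = G = 1.0 to 1.5 mm.
- Difference in bone: (−R) − (−R) = 0.

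Resorption cancels. The arm difference therefore does not depend on the value of R, only on R being equal in the two arms and on G lying on the scanned surface.

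**Illustration 2: would such a difference be declared significant?**

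Section 12.0 says earlier work on mucosal levels could distinguish 0.5 mm in groups of 25. I assume a two-sided alpha of 0.05, 25 per group and a range of power for that earlier work, and use the normal approximation.

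SD = 0.5 / [(1.96 + z) × √(2/25)], where z is the normal quantile for the assumed power:

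- 50% power: SD = 0.90 mm
- 80% power: SD = 0.63 mm
- 90% power: SD = 0.55 mm

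With 20 per group, power = Φ(d / [SD × √(2/20)] − 1.96). For d = 1.0 mm this gives 93.9%, 99.9% and above 99.9% respectively. For d = 1.5 mm it is at least 99.9% throughout.

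Under these assumptions, a purely mucosal gain of the anticipated size would very probably be significant on an outcome named ridge volume. These are linear figures for mucosal levels. The primary outcome is a volume, for which no SD is given, so they show direction only.

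**The case against.** The strongest defence is that the protocol supplies its own operational meaning. Section 2.0 says that intraoral scanning can measure ridge volume, so the outcome may be read as scanned ridge contour. That convention would be harmless if treatment left the mucosa alone. Here the randomised treatment is designed to thicken it, so the sentence does not resolve the mismatch. It does mean that a usable quantity is being measured.

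The second defence largely stands. Soft tissue is the evident target throughout: section 1.0 speaks of mucosal volume, section 2.0 presents 3D measurement as a way to assess soft-tissue augmentation, section 3.0 asks about the health and appearance of oral tissues, and section 12.0 reasons from mucosal levels. Marginal bone level is a separate outcome.

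A reader might therefore infer more than the documents support, in three ways:

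- **That the trial plans to claim preserved bone from the primary result.** No section plans this.
- **That the primary comparison is invalid or cannot be obtained.** The scan can measure contour, and the randomised comparison of contour is sound.
- **That the protocol's millimetre figures fix where each arm's surface will end up, or that a small difference could come from bone alone with no graft retained.** The documents give no axis, do not say whether the augmentation is net of resorption, and describe no case of a graft leaving no residual bulk.

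**Conclusion.** The concern holds as a defect in how the primary outcome is named and defined, and in what may be concluded from it. As written, a mucosal gain would be reported as a ridge-volume effect. With equal bone loss in both arms and the anticipated augmentation lying on the scanned surface, the contour difference would be 1.0 to 1.5 mm and the bone difference zero. That figure rests on those two assumptions and on a linear scale, so it is not a prediction of the volume result.

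The concern does not call into question the choice of instrument, the randomisation or the validity of the contour comparison. The plan should be corrected because the remedy costs almost nothing and the present wording invites a misreading.

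**What to change.** In section 6.0, restate the primary outcome as the change from the visit 1 scan to the 12-month scan in peri-implant tissue contour volume (mucosa plus underlying bone), in a fixed buccal region on superimposed scans. Section 4.0 admits patients whose tooth is still to be extracted, so define the region to exclude the tooth crown where the tooth is present at visit 1.

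State that the primary result supports conclusions about contour only, and that conclusions about bone rest only on radiographic marginal bone level. None of the six visits described in section 6.0 lists the peri-apical radiographs, so their timing must be added.

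Use the same term in sections 2.0 and 12.0. Section 7.0 says "CBCT and other 3D intraoral scanner capture light-generated images", while the first-visit text in section 6.0 describes CBCT as an image of the jaw bones and the sixth-visit text limits the light-based description to intraoral scans. These three statements should be reconciled.

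Cost: both scans are already scheduled, so the primary outcome needs no new measurement. The work is rewording, a region definition and a place in the schedule for the radiographs. The downside is a narrower claim.
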